5.6. Medication Modification

5.6.1 Medication Modification for Myalgias

Grade 1 Myalgias – If needed patient may take NSAIDs/analgesics at the discretion of the treating physician. Frequently this type of skeletal pain is not relieved with these medications.

Grade 2 or 3 Myalgias - Study medication should be held and patient instructed in the use of NSAIDs/analgesics per treating physician orders. ALT, AST and CK should be drawn within 24 hours.

- If labs are in acceptable range (ALT and AST are $< 3 \times \text{ULN}$ and CK $< 2.5 \times \text{ULN}$) study medication should be resumed.
- If Grade 2 or 3 myalgias redevelop, study medication should be discontinued. Patient will be considered off study medication but will continue to be followed.
- If ALT and/or AST are $> 3 \times \text{ULN}$ and/or CK $> 2.5 \times \text{ULN}$ study medication should be discontinued. Patient will be considered off study medication but will continue to be followed.

Any patient with suspected rhabdomyolysis/compartment syndrome of lower leg or rupture of tendon should stop the study medication immediately. The treating physician should assess the patient and order CK isoenzymes and/or other labs as deemed necessary. Patient will remain on study (off study medication) and be followed as usual.

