5.7 Adherence

5.7.1 Adherence will be estimated as: 1) the proportion of expected pills taken while on treatment and 2) the proportion of the total number of pills that could be taken if the participant completed the study. We will calculate and report the mean adherence across all individuals as well as the proportion of patients who were 75% adherent (using both definitions of adherence). The primary analyses will include all randomized participants, regardless of adherence. Secondary analyses will be done using participants who were at least 75% adherent, separately using each definition.

5.7.2 To determine patients' adherence with the study agent, a medication diary will be utilized. It will be given to the patient by staff with instructions on how to complete. Every other month, medication diaries will be collected to verify medication usage. In addition, at 6 and 24

[figure not shown]
months any remaining bottle(s) of study agent will be collected from the patient and a pill count will be performed to verify the patient-recorded information in their medication diary.

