6.9. Unblinding Methods

In the event a patient on this study develops a toxicity (adverse event or severe adverse event) for which the patient's physician or other health care professional feels that it is in the patient's best interest to know what drug they are taking (active study drug or placebo), the following procedure should be followed:

- Step 1: The patient's physician or a designated health care professional should call the Wake Forest University Baptist Medical Center Physician Access Line at [contact] and ask that [name], Director of the WF NCORP Research Base, be contacted immediately either in his office, by pager, or at home. In the event [name] cannot be reached, the PAL operator should contact [name], Director, Symptom Treatment Protocols, in her office, by pager, or at home. If neither [name] nor [name] can be reached, the PAL operator should contact [name], Co-Investigator, in his office, by pager, or at home. If [name], [name] or [name] cannot be reached, the PAL operator should contact [name], Co-Investigator, in his office, by pager, or at home.
- Step 2: Once contact has been made, the patient's physician or health care professional should explain the reason for the request to unblind the treatment arm that the patient is on. If the Research Base representative feels that the toxicity (AE/SAE) is possibly, probably or definitely related to the study drug, then the next step will be followed.
- Step 3: The responsible Research Base representative will call the pharmacist @ Biologics, Inc. ([contact]). There is an "on-call" service provided 24 hours a day, seven days a week for the Chemical Drug Trials unblinding service. The Biologics pharmacist may contact the patients' physician and/or health care professional directly with the unblinding information. Written documentations of the unblinding process will be sent to the Research Base Principal Investigator by Biologics, Inc.
- Step 4: In the event that the patient's treatment is unblinded, that patient will be taken off study with no further study follow-up. Appropriate procedures for grading toxicities, assigning causality, and reporting severe adverse events (if applicable), should be followed. The event will be reviewed by the WF NCORP Safety and Toxicity Review Committee and reviewed by the NCORP Research Base Data Safety and Monitoring Board.

Record the details of the adverse event and/or unblinding in the site source documentation and complete appropriate AE forms.

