7.8. Off Treatment Criteria

Participants may stop taking atorvastatin for the following reasons: completed the protocol-prescribed intervention, adverse event or serious adverse event, inadequate agent supply, concomitant medications, medical contraindication, or interruption of chemotherapy due to adverse events or death.

Participants will continue to be followed, if possible, for safety reasons and in order to collect endpoint data according to the schedule of events. The study is designed to account for drop-outs due to poor health or death or loss to follow-up; thus, there will be no replacement of subjects that must drop out of the study after enrollment.

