12.3. Analysis Plan

The primary hypothesis for Specific Aim 1 is that statin use will protect against a harmful reduction in LVEF measured over 24 – 27 months for patients with breast cancer or lymphoma who receive Anthracycline-based therapy. All randomized patients will be used in the analysis to compare groups (“intent to treat” approach). Since LVEF is measured on a continuous scale and this is a randomized trial, our primary analysis will fit an analysis of covariance (ANCOVA) model that compares the 24- 27 month values of LVEF between groups adjusting for the baseline (pre-treatment) levels of LVEF and stratification factors. Note that patients are stratified by planned dose and that is the stratification that will be used in the analysis, even if the patient ends up getting a different dose. This analysis will address the first specific aim.

To address the second primary aim, we will examine whether the early treatment effect of statin use (6 months post randomization) predicts the long-term (24 – 27 month) effect of statins. Pilot data (Section 2) suggest that Anthracycline-based therapy injury occurs early and concomitant statin use attenuates this early Anthracycline-based therapy-mediated injury. We will fit an ANCOVA model that compares the 24- 27 month LVEF values for the treated and control groups and will also include covariates for the baseline LVEF and 6-month change in LVEF values. We will examine the treatment by 6-month LVEF change interaction to determine whether the correlation between early and late changes in LVEF differs by treatment. Thus, this model will have 4 terms of interest: the main effect for treatment, the main effect for the change in LVEF after 6 months, the main effect for baseline pre-treatment LVEF, and the treatment by change in LVEF after 6-month interaction. If the interaction is non-significant, we will examine the model with the 3 main effects. Since there may be limited power to test this interaction, we will use a 0.15 threshold for testing significance of the

interaction term in the model.

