12.4. Potential Analytic Concerns in Primary Efficacy Analyses

Lost to Follow-up: We designed this study to recruit 278 total patients so that 200 are available at the end of the study. Thus, we will need to consider how to analyze data from the 78 patients who may drop out. To examine whether the missing data are either missing completely at random or missing at random, we will compare the baseline characteristics of those who drop out and those who complete the trial. If there is no evidence of informative missing data, analyses will be done using the repeated measures ANCOVA with a mixed models approach (PROC MIXED in SAS). However, if there is evidence that the missing data are informative and treatment-related (e.g. if there are fewer dropouts in the statin group or if missingness is related to other medical outcomes that are strongly associated with the outcome of interest) and not MAR, then we will use more sophisticated statistical methods.⁷⁸⁻⁸⁰ One possible approach is to model the probability of dropping-out for each participant conditional on their baseline characteristics and treatment assignment. These probabilities would then be used to stratify participants (both completers and drop-outs) before making treatment comparisons. Thus each stratum would contain participants with similar predicted probabilities of trial completion (although only a subset would be completers). The final treatment effect estimates could be made using the completers with weights assigned to them based on the ratio of drop-outs to completers within each stratum. This approach and other methods for handling missing data have been previously described by [name].⁷⁸⁻⁸⁰

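### Section 6.9 Step 4 ends endpoint collection after a toxicity-related unblinding, creating avoidable and potentially informative missing LVEF, probably small in amount

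*Combined protocol and SAP*

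**What the plan says.** Section 6.9 sets out emergency unblinding in four steps. Under Step 2 the process goes ahead only if the Research Base representative "feels that the toxicity (AE/SAE) is possibly, probably or definitely related to the study drug". Under Step 3 the pharmacist may contact the patient's "physician and/or health care professional directly with the unblinding information". Step 4 then states that "that patient will be taken off study with no further study follow-up". No other section makes an exception. Step 4 does keep toxicity grading, causality, serious adverse event reporting and committee review in place, and 10.3 asks for follow-up of Grade 4 and 5 events related to the intervention.

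On the analysis, 12.3 says "All randomized patients will be used in the analysis to compare groups" and specifies an ANCOVA on LVEF at 24-27 months, adjusted for baseline LVEF and the stratification factors. Section 5.7.1 says "The primary analyses will include all randomized participants, regardless of adherence".

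On follow-up after stopping drug, 7.8 includes adverse events among the reasons for stopping and says "Participants will continue to be followed, if possible, for safety reasons and in order to collect endpoint data". Section 5.6.1, on stopping for recurrent myalgia or raised laboratory values, says "Patient will be considered off study medication but will continue to be followed". Section 7.9 lists an adverse event or serious adverse event among the reasons a participant may go off study.

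**The concern.** The primary outcome is one late MRI measurement. A patient unblinded before that scan cannot supply it, because the protocol itself ends the visits. These patients are selected by a perceived drug toxicity that occurred after randomisation. If atorvastatin causes more such events than placebo, or if patients with these events have a different LVEF course, the missing values are related to arm, to outcome, or to both.

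Most dropout is outside the trial's control. This loss is not: the scans are already in the schedule, and 7.2 says the MRI results are not reviewed at the site, so a site's knowledge of the code need not reach the LVEF reading. At stake is a small part of the protection that randomisation gives the primary comparison, together with the later cognitive, self-reported and biomarker data of the same patients.

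**Working it through.** **Passages side by side**

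| Situation | Section | Endpoint follow-up |
|---|---|---|
| Drug stopped for an adverse event | 7.8 | Continues, if possible |
| Drug stopped for myalgia or raised laboratory values | 5.6.1 | Continues |
| Adverse event as an off-study reason | 7.9 | May end |
| Unblinded for a possibly related toxicity | 6.9 Step 4 | Ends, with no discretion |

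The same toxicity can fall under more than one row. Whether the patient is scanned at 24-27 months then depends on whether someone asked for the code.

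**The plan's own figures (12.6)**

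Inputs: SD 7.7, correlation 0.5, two-sided alpha 0.05, 80% power, 100 per group.

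- Detectable difference = 7.7 × √(2 × (1 − 0.5²)) × (1.960 + 0.842) / √100 = 2.64. This matches the table.
- Adjusted SD = 7.7 × √0.75 = 6.67. Power at 2.64 with 100 v 100 is 79.9%.
- Planned loss: 78/278 = 28.1%.

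**Possible shift in the treatment difference**

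The documents give neither an unblinding rate nor the LVEF gap between lost and kept patients, so both are assumptions. Let fS and fP be the shares of the statin and placebo arms lost through Step 4, among those who would otherwise have a final scan. Let g be the mean LVEF gap between kept and lost patients, taken as equal in both arms and of unknown sign.

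Shift = (fS − fP) × g

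The value g = 2.64 is the plan's detectable difference, used only as a scale.

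| Lost, one arm v the other | g | Shift (points) | Share of 2.64 |
|---|---|---|---|
| 1% v 0% | 2.64 | 0.03 | 1.0% |
| 2% v 0% | 2.64 | 0.05 | 2.0% |
| 2% v 1% | 2.64 | 0.03 | 1.0% |
| Equal rates | 2.64 | 0 | 0% |
| 1% v 0% | 8 | 0.08 | 3.0% |
| 2% v 0% | 8 | 0.16 | 6.1% |
| 5% v 0% (stress case) | 8 | 0.40 | 15.2% |

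For a shift of 10% of 2.64, that is 0.264 points, the gap would have to be 0.264/0.01 = 26.4 points at 1% lost, or 0.264/0.02 = 13.2 points at 2%.

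**Possible loss of power**

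This applies only if the losses come on top of the 28% allowance. At a difference of 2.64, 98 v 100 gives 79.5% and 98 v 98 gives 79.1%. If the allowance already covers these patients, power does not fall.

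**The case against.** The strongest defence has four parts.

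- **Sections 7.8 and 5.6.1 deal with stopping drug, not with breaking the blind.** Section 7.8 also says only that follow-up continues if possible, and 7.9 permits going off study for an adverse event. Step 4 can be read as a specific rule consistent with 7.9. This largely stands: the sections are in tension and need reconciling, but they do not flatly contradict each other. The difference that remains is that 7.9 permits what Step 4 makes mandatory.
- **Sections 12.3 and 5.7.1 define who is analysed, not whose data are complete.** This also stands. Step 4 does not remove anyone from the analysis set or discard values already collected, and a 6-month scan could still enter the mixed model.
- **Section 12.4 already anticipates 78 patients without final data.** It names treatment-related missingness, and missingness tied to other medical outcomes, as triggers for other methods. This stands in part. The one method it describes, "One possible approach is to model the probability of dropping-out for each participant conditional on their baseline characteristics and treatment assignment", does not use the toxicity itself, which arises after baseline, and the mixed model relies on data missing at random. Neither is as good as having the scan.
- **Few patients are likely to be affected.** A clinician must want the code, the Research Base must judge the event at least possibly related, and 5.6 manages ordinary toxicity without unblinding. This is reasonable and governs the size of the point.

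A reader might also cite 7.9, which keeps open-label statin users in the rest of the trial, as a precedent for retaining unblinded patients. It is not one: those participants start a non-study statin, and nothing says that their randomised assignment is disclosed.

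**Conclusion.** The point holds as avoidable, potentially informative missing data created by a rule in the protocol. At an assumed 1-2% loss in one arm only, with a 2.64-point gap, the shift is 0.03 to 0.05 LVEF points in an unknown direction, and power falls by at most 0.8 percentage points. Material bias is unlikely at such rates. The larger shifts in the table need rates or gaps for which the documents offer no basis.

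A reader might infer two stronger conclusions that the documents do not support. One is that Step 4 contradicts the intention-to-treat analysis; it reduces the data available to that analysis without changing who belongs in it. The other is that all follow-up stops, safety included; Step 4 itself and 10.3 show that safety reporting goes on. The point covers emergency unblinding during the study only, not the release of codes at study completion, which 6.9 handles separately.

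**What to change.** - **Amend 6.9 Step 4.** An unblinded patient who has not withdrawn consent stays in the scheduled outcome assessments, including the 6-month and 24-27 month MRI, and is analysed in the randomised arm. Whether study drug continues is for the sponsor to decide.
- **Reconcile 6.9, 7.8 and 7.9** so that they agree on when endpoint collection ends.
- **Contain the code.** State that the assignment is not passed to the central MRI readers or, where possible, to the cognitive examiners, whom 7.2 requires to be blinded. Step 3 makes this necessary, because the code may go straight to the treating clinician.
- **Flag unblinded patients** and show the cognitive and self-reported outcomes with and without them.
- **Report unblindings by arm**, including patients already removed, and state for each whether a 6-month or final scan exists.

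The cost is one amendment, a few visits that are already in the schedule, and a site step to contain the code. Section 3.1.1 indicates that the remaining participants were approaching their final assessment, so the amendment protects only scans still to come. The reporting by arm is useful for every patient, whatever the stage of the trial.

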10.1 Protocol Specific Reporting for Serious Adverse Events (SAEs)

DEFINITION: ICH Guideline E2A and Fed. Reg. 62, Oct. 7, 1997 define serious adverse events as those events which meet any of the following criteria?

- Results in death

- Is life threatening (Note: the term life-threatening refers to an event in which the patient was at risk of death at the time of the event; it does not refer to an event which hypothetically might have caused death if it were more severe).
- Requires inpatient hospitalization or prolongation of existing hospitalization
- Results in persistent or significant incapacity or substantial disruption of the ability to conduct normal life functions.
- Is a congenital abnormality/birth defect
- Events that may not meet these criteria, but which the investigator finds very unusual and/or potentially serious, will also be reported in the same manner.
- **Grades 4 and 5 expected (solicited) and unexpected (unsolicited) SAEs that meet the above definition for SAEs and/or regardless of attribution (i.e. regardless of whether they are related to this study intervention or not) should be reported to the RB DMC using the FDA Form 3500 (MedWatch).**
- Site staff and/or Principal Investigators will report to the RB Data Management Staff within 24 hours of discovering the details of all unexpected severe, life-threatening (grade 4) and/or fatal adverse events (grade 5) if there is reasonable suspicion that the event was definitely, probably, or possibly related to the study intervention.

Otherwise, the MedWatch should be sent to the RB DMC by fax or email within 10 working days of discovering the details of the SAE.

Data Elements to include on the MedWatch are:

- SAE reported date
- CTCAE Term (v4.03)
- Event onset date and event ended date
- Severity grade (use table provided in Section 10.1.3 below)
- Attribution to study intervention (relatedness)
- Action taken with the study participant and intervention
- Outcome of the event
- Comments

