11.4 Data and Safety Monitoring Board

The Data Safety Monitoring Board meets every six months to review all phase II and phase III protocols. The Board includes members demonstrating experience and expertise in oncology, biological sciences, biostatistics and ethics. The DSMB report is generated by the RB statistician. Areas of review may include the following: Date study Opened; Study Objectives; Patient Accrual; Patient Status and Retention; Study Status; Last Contact Status; Patient Compliance; Number of Biopsies/Labs as needed; Patient Characteristics; Summary of Observed Toxicities; Adverse Events; Date, Event briefly described, Relationship to Drug, Arm assigned; Summary of Primary and Secondary Measures. Following each meeting, WF RB will provide DSMB reports to all accruing sites via the regular weekly email correspondence.

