12.7. Reporting and Exclusions

We will measure the level of compliance in randomized patients. If a patient drops out of the study early due to an adverse event that may be related to statin use, they will be non-compliant for subsequent treatment, and thus still inform the primary endpoint for our analyses, and their outcome will be considered as “non-compliant”. For patients who drop out early due to a non-statin related adverse event or die during the study we will analyze them in the following ways.

First we will conservatively assume that all drop-outs/deaths are non-compliant. Since there is a placebo group in this study we can assume that the rates would be similar between groups and still allow a comparison of compliance rates between groups. Next, we will consider two forms of imputation for secondary analyses. The first will use early compliance data (if available) to determine a compliance rate and that value will be carried forward to the end (i.e., Last observation carried forward) and the second would be to use a multiple imputation procedure to impute final compliance rates for participants based on modeling the compliance rates for those with complete data.

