12.9. Evaluation of Response

All participants will be assessed for compliance once they are randomized to treatment and receive at least one dose of treatment. The primary analysis will consist of all randomized patients who receive at least one dose of study drug. Secondary analyses will consist of patients who either complete the trial (with $\geq 75\%$ compliance) or who drop out for adverse events that are related to the use of statins. Patients who drop out for non-related adverse events or die for reasons not related to statin use will be removed from the secondary analysis. Adverse events described by the Data Safety Monitoring Committee as related to statin use will be differentiated so as to render decisions regarding study drug compliance.

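### Section 6.9 does not require grade and causality to be recorded before the code is broken, so the relatedness of unblinded events can be assigned with the arm known

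*Combined protocol and SAP*

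**What the plan says.** Section 6.9 sets out four numbered steps.

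- **Trigger.** The procedure applies when a patient "develops a toxicity (adverse event or severe adverse event) for which the patient's physician or other health care professional feels" that knowing the treatment is in the patient's best interest. There is no grade threshold.
- **Step 2.** The physician explains the request by telephone. The code break then depends on an opinion from the Research Base, whose contact must be someone who "feels that the toxicity (AE/SAE) is possibly, probably or definitely related to the study drug, then the next step will be followed"; at that point the arm is still unknown.
- **Step 3.** A telephone call goes from the Research Base to the drug supplier's pharmacist, who may then give the result straight to the treating physician or other health care professional. The written record named here documents the unblinding process and is sent by the drug supplier.
- **Step 4.** The patient leaves the study with no further follow-up, and then: "Appropriate procedures for grading toxicities, assigning causality, and reporting severe adverse events (if applicable), should be followed". The instruction to complete the adverse event forms comes after this.

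Section 10.1 makes attribution to study intervention a data element of the MedWatch form, which the site sends in. Reporting is due within 24 hours for unexpected grade 4 or 5 events "if there is reasonable suspicion that the event was definitely, probably, or possibly related to the study intervention", and otherwise within 10 working days of discovering the details.

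Relatedness is used in three later places. Section 11.4 lists "Relationship to Drug, Arm assigned" among the items the monitoring board may review. Section 12.7 treats separately the case "If a patient drops out of the study early due to an adverse event that may be related to statin use". Section 12.9 keeps statin-related drop-outs in the secondary analysis set and removes unrelated ones; "Adverse events described by the Data Safety Monitoring Committee as related to statin use will be differentiated" for that purpose.

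**The concern.** In a double-blind trial, a causality judgement is informative about the drug only if the person making it does not know the arm. Once the arm is known, an event on placebo is hard to record as drug-related, while the same event on atorvastatin readily keeps that label. A site that follows 6.9 in its printed order learns the arm and then grades and attributes the event.

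The Step 2 gate gives the risk a direction. Every event that reaches Step 3 has already been judged at least possibly related. After disclosure there is little room to move the label upward, and a move downward would be expected mainly on placebo. Such selective re-labelling would show an excess of related toxicity on atorvastatin that the drug did not cause.

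**Working it through.** The plan states no figure on this point, so the check is a reading of the sections against each other, followed by a bounded illustration.

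**Is anything fixed before the code is released?**

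1. *Step 2 opinion.* It is blinded and comes before the code break, but it belongs to the Research Base representative and serves as a gate. Section 6.9 does not say that it is written down, that it carries a grade, or that it is the attribution of record.
2. *Site's grade and causality.* Section 6.9 first mentions these in Step 4. Sections 10.1 to 10.3 say what to report, how to grade, and how to follow up. None of them says that attribution must precede unblinding.
3. *Reporting clock.* It runs from discovery of the event's details. Ten working days leaves ample time for disclosure to come before the form is completed.
4. *Order.* Step 4 does not say that the assessment must wait until after disclosure. A site may have graded and attributed the event already. The text permits arm-aware attribution; it does not compel it.

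**Where does the label go?**

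| Use | Depends on relatedness? |
|---|---|
| Primary LVEF analysis (12.3, 12.9) | No |
| Related-toxicity summaries and board listings (11.4) | Yes |
| Compliance, first analysis (12.7) | No: all drop-outs and deaths count as non-compliant |
| Compliance, secondary imputations (12.7) | Yes |
| Secondary analysis set (12.9) | Yes, by way of the Data Safety Monitoring Committee's attribution |

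Patients unblinded under 6.9 have no further follow-up. Unless unblinding comes after the final MRI, they have no 24–27 month LVEF, so their label cannot change who contributes to a secondary ANCOVA at that time point. At most it affects the use of their 6-month value in a repeated-measures model.

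**Illustration of size.** Inputs: 278 patients randomized 1:1 (Sections 5.2 and 12.1), hence 278/2 = 139 per arm. Assumptions: k code breaks in each arm, all judged at least possibly related at Step 2, and a share s of the placebo events re-coded as unrelated after disclosure. The documents give neither k nor s.

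Artificial difference in the related-event rate = k × s / 139.

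| k per arm | s = 0 | s = 0.5 | s = 1 |
|---|---|---|---|
| 2 | 0 | 2 × 0.5/139 = 0.7 points | 2/139 = 1.4 points |
| 5 | 0 | 5 × 0.5/139 = 1.8 points | 5/139 = 3.6 points |
| 10 | 0 | 10 × 0.5/139 = 3.6 points | 10/139 = 7.2 points |

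The difference is zero if the blinded judgement is kept as the record.

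**The case against.** The strongest reply is that a blinded causality judgement already exists, because the code cannot be broken under 6.9 without the Step 2 opinion. Step 4 then merely points to the usual reporting procedures and does not say they begin only after disclosure. In addition, grade 4 and 5 events meeting the serious-event definition are reported whatever their attribution, so none is lost. Section 12.9 relies on the Data Safety Monitoring Committee and not on the site's entry. All of this is correct and it narrows the point. It does not close the gap, because the Step 2 opinion need not be recorded or retained. Nor do the documents say that the Committee attributes events blind; its review items list relationship and arm together.

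Three stronger readings are tempting, and the documents do not support them.

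- *That recorded relatedness is biased.* The text shows that arm-aware attribution is possible. It gives no evidence that it happens, or how often.
- *That the most important toxicities are affected.* The trigger has no grade threshold, and serious events that never prompt unblinding are outside this procedure.
- *That a spurious significant excess would follow.* Six related events against none, with 139 per arm, gives a two-sided Fisher p of 0.030. That requires every placebo event and no atorvastatin event to be re-coded, and no related event in any other patient. Re-coding half the placebo events gives 6 against 3, p = 0.50. Keeping full re-coding but adding an assumed 8 other related events per arm (8/139, about 6%, the myalgia rate listed in 6.2) gives 14 against 8, p = 0.27. The plan also specifies no between-arm test of related toxicity.

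**Conclusion.** The gap is real and limited. Section 6.9 names grading and causality after the code break and secures no blinded record beforehand, so for events unblinded by this route the recorded relatedness can be arm-aware and could be downgraded selectively on placebo. The size cannot be derived from the documents. Under the stated assumptions it runs from zero to 1.4, 3.6 or 7.2 percentage points for 2, 5 or 10 code breaks per arm. What is exposed is the related-toxicity summaries, the monitoring board's listings and the secondary sorting in 12.7 and 12.9. The conclusion on LVEF in the primary analysis does not depend on it. The point deserves correction because the remedy costs almost nothing and the blinded judgement cannot be recovered once the arm is known.

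**What to change.** In Section 6.9, move the grading and causality requirement ahead of Step 3. Before the call to the drug supplier, a dated CTCAE grade and causality should be on record: the site's own, or at minimum the Research Base representative's Step 2 opinion in writing. State that this requirement must not delay disclosure in an emergency.

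Use the blinded attribution in the toxicity tables, and supply it to the Data Safety Monitoring Committee as the basis for its determination under 12.9. The Committee should remain the adjudicator there; letting the site's entry govern instead would change the analysis plan and is not needed. Log any revision made after unblinding in a separate field, so that both values can be shown.

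The cost is about a minute of recording before the call, one additional form field, and a sentence in 6.9 and in 12.9.
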